#### 4.1.2 C11-AMT PET scan co-registered with CT scan without IV contrast

C11-AMT PET will be performed before starting pembrolizumab treatment and at least 24 hours after FDG PET/CT scan. This test will be performed at the PET/CT scanner available at the Biomedical Research Imaging Center (BRIC). Please note that due to the short half-life of the C11-AMT tracer (20 minutes) and the need to perform dynamic imaging, C11-AMT PET scan may not be whole body and can be limited to only 1 or 2 bed positions, at the discretion of the radiologist depending on where the metastatic lesions of interest are anatomically located and should be similar to the area scanned with FDG PET to ensure ability to correlate baseline FDG PET and baseline C11-AMT parameters, and encompasses target lesions as described in section 6.7.2. Subjects will remain in the scanner continuously from the time of injection to target time for imaging 5 – 50 minutes following the injection. PET data will be acquired during the initial phase following the injection to determine whether or not 30 min images reflect steady-state distribution. Images acquired 20-40 min (+/- 5 min) following the injection will be used for data analysis purposes. For subjects who cannot be imaged with a single bed position, two bed positions will be utilized and images acquired using alternating bed positions. CT scan without IV contrast will be co-registered with C11-AMT PET to assist in defining regions of interest (ROI) for downstream AMT PET analysis. **If for whatever reason C11-AMT was not produced appropriately or the PET scan failed, patients may undergo a repeat C11-AMT PET scan.** Participants from affiliate sites must have their C11-AMT PET scan performed at UNC-CH. The following steps describe synthesis, quality control testing, administration, and analysis of AMT PET scan.

##### 4.1.2.1 Synthesis of $\alpha$ -[11C]-methyl-L-tryptophan

The protocol for C11-AMT production is based on a simplified 2-step hydrolysis procedure that has been previously extensively applied for routine clinical use [70]. The product will be manufactured [name] group at the Translational Imaging Core, BRIC, where a cyclotron and radiochemistry modules are in place to ensure semi-automated radioisotope production under Good Medical Practice (GMP) guidelines. Given the short half-life of C11-AMT, it will be produced on the same day immediately before the AMT PET imaging. This method eliminates the need for high performance liquid chromatography (HPLC) isolation and purification of the final product, thus saving considerable time and eliminating potential pyrogenicity and production contamination problems associated with the multiple reuse of a semi-prep HPLC column. Five elements are important in this process: First, lithium diisopropylamide (LDA), which is required for the first step, will be freshly made within a week from the actual AMT production; alternatively, it can be purchased. Second, the AMT precursor, (dimethyl 2(S), 3a(R), 8a(S)-(+)-hexahydro-8(phenylsulfonyl)pyrrolo[2, 3-b]indole-1,2-dicarboxylate) will be purchased from a commercial vendor (Sigma-Aldrich) and stored at 4°C. An aliquot will be thawed to room temperature for 30-60 min on the day of C11-AMT synthesis. Third, production of  $^{11}\text{CH}_3\text{I}$ . [ $^{11}\text{C}$ ]Carbon dioxide will be produced by the  $^{14}\text{N}(\text{p},\alpha)^{11}\text{C}$  reaction from the GE PETtrace 880 Cyclotron (Biomedical

Research Imaging Center, UNC-CH). [ $^{11}\text{C}$ ] methyl iodide will be prepared using the GE FX-FN module, by converting [ $^{11}\text{C}$ ]  $\text{CO}_2$  to [ $^{11}\text{C}$ ]  $\text{CH}_4$ , followed by iodination. Fourth, production of C11-AMT will be performed from its precursor and other molecules (LDA,  $^{11}\text{CH}_3\text{I}$ , THF, TFA, KOH), as shown in Figure 4. Fifth, C11-AMT will be purified using commercially available C-18 Sep-Pak cartridges.

**Figure 4. Procedure for Synthesis of  $\alpha$ -[ $^{11}\text{C}$ ]-methyl-L-tryptophan.**

Abbreviations: LDA: lithium diisopropylamide; THF, tetrahydrofuran; TFA, trifluoroacetic acid; C-18 Sep-Pak, solid phase extraction chromatography cartridges. Adapted from[70]

#### 4.1.2.2 Quality control analysis of $\alpha$ -[ $^{11}\text{C}$ ]-methyl-L-tryptophan prior to administration

Immediately following preparation the C11-AMT product solution will undergo a series of quality tests to ensure the product is suitable for human administration. Release of the product for human use will be the responsibility of [name] group, Radiopharmacist at the BRIC. More specifically, radiochemical purity will be performed by radio-HPLC to ensure greater than 90% of the radioactivity is in the proper chemical form (C11-AMT). Visual inspection to evaluate for particulates will be performed on each batch. The pH of the solution will be measured and adjusted using 8.4% sodium bicarbonate and 23.4% sodium chloride, if necessary. Osmolality will be evaluated via an osmometer. Residual solvents will be assessed via gas chromatography to ensure chemicals used to clean the reaction vessel have been properly removed. The product will also undergo sterility and pyrogenicity testing. A filter integrity test will provide an immediate indication of the sterility of the batch, and an endotoxin test will confirm the lack of pyrogens. Samples from the batch will also be inoculated and monitored for full sterility analysis. Table 1 below summarizes the required tests and the specifications for release.

QUALITY CONTROL TEST	DESCRIPTION	REQUIREMENTS FOR PASS	REQUIRES TEST PASS PRIOR TO PRODUCT RELEASE
Chemical Purity	Visual inspection for color and particulates	Clear and Colorless	Yes
Filter Integrity	Test bubble point	Meet pressure specified by manufacturer	Yes
pH	pH as per USP test method 791	5.0 – 7.5	Yes
Chemical & Radiochemical Purity	HPLC consistent with guidelines of General Chapter <621>, Chromatography subsection HPLC	Radiochemical Purity > 95% Other UV (list nm) peaks ≤ 35 µg in final product	Yes
Radiochemical Purity	TLC	Rf > 0.5 and Purity ≥ 95%	Yes
Residual Solvent Levels	Gas Chromatography	Acetone < 5,000 ppm Acetonitrile < 400 ppm	Yes
Radionuclidic Purity	Half-life Determination	18.4 – 22.4 min	Yes
Bacterial Endotoxin Levels	Limulus Amoebocyte Lysate (LAL) by PTS	< 175 EU per dose	Yes
Sterility	USP <71> sterility test	No growth observed in 14 days	No

**Table 1. Summary of quality control tests required prior to release of radiopharmaceutical product for human studies.** Abbreviations: USP, United States Pharmacopeia; HPLC, high pressure liquid chromatography; TLC, thin layer chromatography; Rf, relative front (measure of solubility); ppm, parts per million; EU, endotoxin units.

#### 4.1.2.3 Administration, scanning and analysis of α-[11C]-methyl-L-tryptophan

Patients will fast for at least 6 hours before the C11-AMT PET study to ensure stable plasma levels of tryptophan and large neutral amino acids. Initially, a venous line will be established for the administration of C11-AMT, irrespective of whether the patient already has a central line (e.g. Mediport, Port-a-cath, PICC line). In other words, these central lines will NOT be used for infusion of the radionuclide agent. Intravenous administration of C-AMT [6.5mCi, maximum 7.15mCi, which is within the 10% variation from the standard dose] will be administered under the supervision of [name] or another qualified nuclear medicine physician from the Nuclear Medicine Department. C11-AMT PETv imaging will commence 5-50 minutes following injection. A low-dose scout CT scan (120 kVp, 10 mA) will be initially acquired for patient positioning and determining dose modulation parameters. CT scan (120 kVp, automated dose

modulation, dose-equivalent of 100 mAs) will be subsequently acquired for attenuation correction and anatomic localization. This scan takes less than 20 seconds and will be performed with the patient suspending respiration in the end-tidal volume phase. This will provide the most accurate alignment of the PET and CT images. The automated CT tube current modulation allows the scanner to adjust the tube current (and therefore CT dose) during the scan and enables the desired image quality to be maintained using the lowest dose possible. The acquisition time for each bed position on the PET emission scans will be adjusted during the scan to optimize the count statistics (i.e. progressively longer acquisition time for later bed positions). PET images will be acquired using 3D acquisition with time-of-flight. Given the short half-life of C11-AMT it may not be possible to perform whole body C11-AMT imaging. Depending on the anatomic location of the tumors, at least 1 or 2 bed positions will be performed instead. These bed positions may not be contiguous but rather include the tumors of interest based on the following three parameters: (a) tumors must have been previously imaged by both CT scan with IV contrast as well as FDG-PET, to ensure correlation between FDG-PET parameters, precise measurements by CT scan with IV contrast, and C11-AMT PET parameters, (b) tumors that are included in assessing antitumor response to pembrolizumab by RECIST criteria are included, (c) the index tumor lesion that has been previously selected for biopsy or surgical excision is included.

Melanoma tumors will be visually identified conjointly by the CT scan and C11-AMT PET images. To objectively determine the tumor region of interest (ROI), we will initially determine the voxel with the highest  $^{11}\text{C}$ -AMT tracer concentration as well as background regions in close proximity to the location of the tumor. Using commercial software (MimVista), the PET data will be evaluated; proposed study parameters include: standardized uptake value ( $\text{SUV}_{\text{max}}$ ) at each lesion, total tumor metabolic volume (TMV) to reflect tumor burden over all lesions, and measurements of intra-tumoral and inter-lesional heterogeneity.

Following completion of C11-AMT PET imaging, biopsy of the tumor tissue that was ideally PET imaged by both FDG and C11-AMT will be performed either by excisional or CT-guided biopsy.

[figure not shown]
The selection of the lesions targeted for biopsy will be determined in part by the location and ability to access safely as well the imaging properties ( $^{11}\text{C}$ -AMT uptake). The lesion selected for biopsy will be documented and annotated on cross sectional images to enable the most accurate correlation between imaging and histopathology.

#### **4.1.3 Fresh Biopsy Collection**

Biopsy of tumors of interest will be performed following C11-AMT PET imaging and before pembrolizumab administration. Depending on tumor location, biopsies can be excisional (the preferred method), punch (acceptable), or core biopsies using an 18g needle. When possible, the biopsy site will be documented with imaging, to enable

precise correlation of local C11-AMT PET parameters with histopathology. Excised tumors will be fixed in formalin and paraffin-embedded for the histopathologic studies outlined above (Section 1.5).

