## 1.6 Correlative Studies

Under this, patients who participate in this trial will be asked to undergo mandatory fresh biopsies at baseline, namely before initiation of pembrolizumab and after C11-AMT PET imaging. Patients with metastatic lung disease (M1b), the metastatic melanoma subgroup with the highest clinical benefit from pembrolizumab[48], may be enrolled in the trial but will only undergo optional biopsies given the high risk (up to 20%) of pneumothorax. “Mandatory” means that it would occur irrespective of prior available tumor tissue. “Research” means that no diagnostic report will be generated; also, it has to occur in previously imaged tumor with all three modalities (FDG PET, C11 AMT PET, and CT scan with IV contrast). This will provide a unique opportunity to correlate the PET parameters of the particular tumor tissue that will be biopsied after C11-AMT PET imaging; this is very important due to the heterogeneity in the parameters that has been described among different tumors within the same patient in the lung cancer cohort [66]. Given the specific focus of this trial, we will give the highest priority to first generate representative tissue sections from these tumors to analyze the following by immunohistochemistry and/or 2-color immunofluorescence:

- a. Expression of the two analogous rate-limiting enzymes of the kynurenine pathway, IDO and TDO in melanoma (S100+) and stromal [i.e. hematopoietic cells (CD33+)]. We anticipate that expression of any these two enzymes, or both, will be correlated with SUVmean and the metabolic rate constant,  $k_3$ .
- b. Expression of the rate-limiting enzyme of the indoleamine pathway, tryptophan hydroxylase. We anticipate that tryptophan hydroxylase will not be highly expressed by melanoma (S100+) as opposed to stromal (hematopoietic) cells (CD33+).

- c. Expression of components of system L, the amino acid transporter systems of L-tryptophan, LAT1 and CD98. We anticipate that LAT1 and/or CD98 to positively correlate with  $K_1$  constant.
- d. Expression status of effector T cells (CD8), IDO, and FoxP3+ mononuclear cells using IHC or 3-color immunofluorescence.

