### Key to Time and Events Table

The time interval between informed consent and initiation of pembrolizumab consists of a screening period and a pretreatment period and overall it should not exceed 28 days. The screening period starts from informed consent and ends immediately before C11-AMT imaging and biopsy which will be performed at UNC Main Campus. This period of C11-AMT scanning and research biopsy are inclusively called the “pre-treatment period.” During the pre-treatment period, the procedure for fresh biopsy collection will also be performed at UNC. Patients must be deemed eligible prior to entering the pre-treatment period. During the screening period patients will be assessed for eligibility based on history, physical examination, inclusion/exclusion criteria, and blood work. Baseline standard of care radiographic imaging will be performed taking into account timing and type of radiographic imaging prior to study enrollment. Based on the pattern and anatomic location of tumors decisions regarding the bed positions that will be held during the C11-AMT PET imaging session as well as the optimal method and location for fresh biopsy collection are made. Finally, the eligibility will be reviewed by the UNC study coordinator and signed off by the Principal Investigator and Multicenter Project Manager. Submission of source documents will be required at least 4 days before C11-AMT PET imaging is performed. The pre-treatment period starts from the day of C11-AMT PET imaging and ends with initiation of pembrolizumab. It involves assessing the quality of C11-AMT PET imaging with the option to repeat once more if necessary. During the pre-treatment period the procedure for fresh biopsy collection is performed.

Unless otherwise noted, screening evaluations and eligibility packet submissions will be completed at a minimum of 4 days prior to C11-AMT PET imaging. Tumor imaging for clinical purposes (i.e. whole body FDG PET coregistered with whole body CT scan with IV contrast) and assessment of clinical response will be performed at least 5 days before C11-AMT PET scan. The serum  $\beta$ -hCG pregnancy test should be done within 14 days of C11-AMT scan and within 72 hours of initiating pembrolizumab treatment in women of childbearing potential. Brain MRI should be obtained within 8 weeks of C11-AMT PET imaging.

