### 6.2.2 Pre-treatment Period

- **Tumor imaging for research purposes:** Baseline tumor imaging should include C11-AMT PET co-registered with computed tomography (CT) of the neck, chest, abdomen and pelvis) with no IV contrast.
- **Fresh tumor biopsy:** Collect a fresh biopsy to support correlative studies. Ideal fresh tumor biopsy type is excisional followed by (in order of preference) punch, followed by core needle biopsy using a 18g needle.

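### Excision, the preferred research biopsy, falls between the baseline CT and the first dose, and Section 6.7.2 does not keep an excised lesion out of the target sum, so surgery alone can meet the response threshold at the first restaging scan

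*Combined protocol and SAP*

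**What the plan says.** **Method.** Section 4.1.3: "Depending on tumor location, biopsies can be excisional (the preferred method), punch (acceptable), or core biopsies using an 18g needle". Section 6.2.2 repeats the ranking: "Ideal fresh tumor biopsy type is excisional", with punch and then core after it.

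**Sequence.** Section 1.6 says of the research biopsy that "it has to occur in previously imaged tumor with all three modalities (FDG PET, C11 AMT PET, and CT scan with IV contrast". Section 4.1.2.3, item (a), says of the lesions in the C11-AMT field that "tumors must have been previously imaged by both CT scan with IV contrast as well as FDG-PET". Footnote 2 to the Time and Events Table says that tumor imaging for clinical purposes and "assessment of clinical response will be performed at least 5 days before C11-AMT PET scan". Footnote 15 places the biopsy at least 24 hours after C11-AMT PET and before pembrolizumab. Baseline CT therefore comes first, then C11-AMT PET, biopsy and first dose. No new baseline CT after the biopsy is specified.

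**Which lesions.** Section 4.1.2.3, item (b), puts the RECIST lesions in the C11-AMT field. Item (c) adds that "the index tumor lesion that has been previously selected for biopsy or surgical excision is included". It does not say that the two must differ. By footnote 1, decisions on bed positions and on "the optimal method and location for fresh biopsy collection are made" during screening. Section 4.1.2.3 also provides a record: "The lesion selected for biopsy will be documented and annotated on cross sectional images".

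**Scoring.** Section 6.7.2 takes all measurable lesions as targets, to a maximum of 5 overall and 2 per organ, and uses their baseline sum as the response reference. Under Section 6.7.3, partial response (PR) is a fall of at least 30% from that sum, and target-level complete response (CR) is the disappearance of all targets. Size-based progression (PD) is a rise of at least 20% and 5 mm over the smallest sum since treatment started.

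**The concern.** The procedure that the protocol prefers can remove a tumor after it has been measured as part of the reference and before any drug is given. Sections 6.7.2 and 6.7.3, applied as written, then score the surgical removal as tumor shrinkage.

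Patients with few targets are eligible. One measurable lesion is enough (Section 6.7.1), disease in a single organ gives at most two targets (Section 6.7.2), and resectable bulky stage IIIB/IIIC disease may be entered at the Principal Investigator's discretion (inclusion criterion 3). The evaluability definition in Section 8.1 does not require that a target lesion remains after the biopsy.

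Week-12 response separates the two groups of the primary comparison (Sections 2.3 and 8.2) and is the numerator of ORR (objective 2.2.1). A false response raises ORR and moves a non-responder into the responder group.

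**Working it through.** **1. The plan's own figure.** Section 8.2 gives 10 responders, 13 non-responders, effect size 1.1, one-sided 0.05 and 80% power. A two-sample t-test has 21 degrees of freedom, noncentrality 1.1/√(1/10 + 1/13) = 2.615 and critical value 1.721. The power is 0.812, so the figure reproduces.

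**2. Surgery alone.** If the excised lesion is a share s of the baseline sum and the rest is unchanged, the sum falls by s. PR is met when 1 − s ≤ 0.7, that is s ≥ 30%. Unequal lesions can meet this even with five targets: for 40, 20, 15, 15 and 10 mm (sum 100 mm), excising the 40 mm lesion gives −40%.

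**3. Surgery plus change in the rest.** With k equal targets, one excised and the others changing by g, the ratio to baseline is (k − 1)(1 + g)/k. PR needs a ratio of at most 0.7, so g ≤ 0.7k/(k − 1) − 1. Size-based PD at the first restaging scan needs a ratio of at least 1.2, so g ≥ 1.2k/(k − 1) − 1 (the 5 mm rule also applies).

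| k | Change from surgery alone | Change in the rest that still scores PR | Growth in the rest for size-based PD, first restaging scan |
|---|---|---|---|
| 1 | −100% (target-level CR) | none left | none left |
| 2 | −50% (PR) | up to +40% | 140% |
| 3 | −33% (PR) | up to +5% | 80% |
| 4 | −25% (not PR) | −6.7% or lower | 60% |
| 5 | −20% (not PR) | −12.5% or lower | 50% |

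**4. Example, first restaging scan.** Two 30 mm targets give a sum of 60 mm. One is excised and the other grows to 40 mm: (40 − 60)/60 = −33%, scored PR. The remaining lesion alone shows (40 − 30)/30 = +33% and +10 mm, which is PD.

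**5. The same example under confirmation.** Section 6.7.5 asks for a repeat study more than 4 weeks later. PR needs a sum of at most 0.7 × 60 = 42 mm. If the 10 mm growth took 12 weeks, four more weeks give 40 + 10 × 4/12 = 43.3 mm (linear) or 40 × (4/3)^(4/12) = 44.0 mm (exponential). If the baseline CT was 28 days before dose 1, the growth took 16 weeks and the results are 42.5 and 43.0 mm. All exceed 42 mm, so PR would not be confirmed and the patient would become stable disease. If the remaining lesion stays at 30 mm instead, the sum is 30 mm at both scans (−50%) and PR is confirmed.

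**6. Effect on the endpoints (the number affected, m, is assumed).** ORR = (10 + m)/23. For power, values were simulated as N(1.1, 1) in 10 responders and N(0, 1) in 13 non-responders. Then m non-responders were relabelled as responders at random, and the pooled one-sided t-test was applied. The expected mean difference becomes 1.1 × 10/(10 + m).

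| m | ORR | Expected difference | Power |
|---|---|---|---|
| 0 | 43.5% | 1.100 | 0.81 |
| 1 | 47.8% | 1.000 | 0.735 |
| 2 | 52.2% | 0.917 | 0.66 |
| 3 | 56.5% | 0.846 | 0.58 |

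**The case against.** **The lesion would not be chosen as a target.** Section 6.7.2 also asks for lesions that can be measured repeatedly and reproducibly. The biopsy site is planned in screening, and Section 4.1.2.3 lists RECIST lesions and the excision lesion as separate items. A careful reader could leave the lesion out on this basis. That stands as a permitted reading, but not as an exclusion: none of these texts says that an excised lesion is not a target, and Section 6.7.2 also favors larger lesions and coverage of all involved organs.

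**Other rules catch it.** In part they do. New lesions, unequivocal non-target progression and growth on examination (Sections 6.7, 6.7.3, 6.7.4) override the target sum, and overall CR also needs the non-target lesions gone. Confirmation, if it governs week-12 ORR, removes cases where the remaining disease grows past the threshold by the repeat scan, as in step 5. Section 6.7.5 is written for best overall response, so its reach is unclear. It does not remove stable or slow-growing cases, because the excised lesion stays absent.

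**The PD distortion is temporary.** This is right. After a first post-excision scan with a sum below baseline, the smallest sum becomes the reference and the ordinary 20% and 5 mm rule applies to what remains.

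**Unseen sources.** Section 6.7 refers to the RECIST paper, and footnote 15 and Section 6.5.1 refer biopsy details to manuals. None was available, and any of them could contain a rule.

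**A stronger reading.** Because Section 4.1.2.3 lets uptake guide which lesion is biopsied, a reader might infer that misclassification follows SUVmax and biases the primary test in a known direction. The documents do not support that. The choice is made within a patient, and nothing links a patient's SUVmax to the chance of a false response. If such a link existed, the bias could go either way.

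**Conclusion.** The concern holds as a gap in the scoring rules. On the supplied text, a measurable lesion within the caps that is excised after the baseline CT remains in the reference sum. Its removal alone meets the PR threshold at the first restaging scan when it is at least 30% of that sum, and target-level CR when it was the only target. Whether this becomes the patient's week-12 response depends on the other lesions and on whether confirmation applies.

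Each false response is worth 4.3 ORR points. How many there would be is not in the documents and could be zero: a case needs excision rather than punch or core, of a target that is large enough, in a true non-responder, with no overriding progression. The power figures for one to three cases illustrate random misclassification and are not a forecast.

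The point should be fixed. The mechanism follows from the text and the remedy is small. Confidence is medium because the RECIST paper and the manuals could not be read.

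**What to change.** Reconcile Sections 4.1.2.3, 4.1.3 and 6.2.2 with 6.7.2 and 6.7.3 by adding one scoring rule to 6.7.2:

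- A lesion removed by excisional biopsy before Day 1 is not a target lesion.
- If it was already selected, it is dropped and, where possible, replaced by another measurable lesion on the same baseline CT within the caps of 5 in total and 2 per organ. The baseline sum is then recomputed.
- Its absence does not count toward CR or PR.

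Add to Section 8.1 that a patient with no remaining measurable target is not evaluable for the primary RECIST comparison and is listed separately. Record the biopsied lesion and the method on the CRF. Apply the rule to patients already treated, using the lesion annotation that Section 4.1.2.3 requires, with a reader who sees neither SUVmax nor outcome. Biopsy method and treatment are unchanged.

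**Cost.** One rule in 6.7.2, one clause in 8.1, one CRF field and a re-read of the excision cases. A few patients may leave the evaluable set. Starting from 10 and 13 at effect size 1.1, power falls from 81% to 79–80% if one is lost (10 v 12: 0.798; 9 v 13: 0.790) and to 73–76% if three are lost (7 v 13: 0.730, up to 10 v 10: just under 0.765).
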